5.1 Volunteer Identification

Healthy volunteers aged 18-50 will be recruited through various media. Care will be taken not to recruit from vulnerable groups (mental health or other capacity issues or those under 18 years old). This will be checked during the screening process.

Volunteers may be recruited by use of an advertisement +/- registration form formally approved by the ethics committee and distributed or posted in the following places:

- On institutional websites where information will be given and the volunteer information sheet will be downloadable or sent to the volunteer upon request
- In public places, including buses and trains, university campus, student bars, halls of residence, health centres etc. with the agreement of the owner / proprietor
- In newspapers or other literature for circulation
- On radio via announcements
- On a website operated by our group or with the agreement of the owner or operator
- As a post on a Twitter, Facebook or other social media account owned and operated by the study research groups

- By email distribution to a group or list only with the express agreement of the network administrator or with equivalent authorisation
- By email distribution to individuals who have already expressed an interest in taking part in any clinical trial at the Southampton NIHR-CRF
- On stalls or stands at exhibitions or fairs
- Via presentations (e.g. presentations at lectures or invited seminars)
- Direct mail-out: This will involve obtaining names and addresses of adults via the most recent Electoral Roll. The contact details of individuals who have indicated that they do not wish to receive postal mail-shots would be removed prior to the investigators being given this information. The company providing this service is registered under the Data Protection Act 2018. Investigators would not be given dates of birth or ages of individuals but the list supplied would only contain names of those aged between 18-50 years (as per the inclusion criteria).
- Southampton NIHR-CRF Database of Healthy Volunteers: We may contact individuals from this database who have previously expressed an interest in receiving information about future studies for which they may be eligible

Volunteers will be sent a copy of the participant information sheet in response to requests for further information. Volunteers will be given a minimum of 24 hours to review the documentation prior to attending a screening visit. A pre-screening call will then be undertaken for those volunteers that still show interest in the study after receiving the PIS. This is one of the standard procedures used by the site for determining basic eligibility for healthy volunteer studies in order to ensure potential participants do not have their time wasted coming for a face to face screening visit if they are definitely not eligible to participate.

5.2 Schedule of events

Table 2. Schedule of events

Attendance Number	1 ^s	2	3	4	5	6	7	8	9	10	11	12 [†]	COVID-19 Testing
Timeline** (days)	≤90	0	1	3	7	14	28	42	56	84	182	365	As required
Time window (days)				±1	±2	±3	±7	±3	±7	±3	±14	± 28	N/A
Informed Consent	Х												
Review eligibility criteria	Х	х					Х						
Vaccination (IM)		Х					Х						
Vital signs^	Х	Х		Х	Х	Х	Х	Х	Х	Х	Х	Х	х
Height and weight	Х												
Telephone/Video call			Х										
Ascertainment of adverse events and con meds		Х	Х	Х	Х	Х	Х	Х	Х	Х	Х	Х	Х
Diary cards provided		Х					Х						
Diary cards reviewed			Х	Х	Х	Х	Х	Х	Х				
Medical History, Physical Examination	Х	(X)		(X)	(X)	(X)	(X)	(X)	(X)	(X)	(X)	(X)	(X)
Biochemistry, Haematology (mL)	5	5		5	5		5	5					5
Exploratory immunology (mL)		50			50	50	50	50	50	50	50	50	up to 50
Nose/Throat Swab													Х
Urinalysis	х												
Urinary bHCG (women only)	Х	Х					х						
HBsAg, HCV Ab, HIV serology (mL)	5												
Blood volume per visit	10	61.5		5	55	50	55	55	50	55	50	50	up to 57.5
Cumulative blood volume [%]	10	71.5		76.5	131.5	181.5	236.5	291.5	341.5	396.5	446.5	496.5	554

S=screening visit; (X) = if considered necessary ^ = Vital signs includes pulse, blood pressure and temperature; ** Timeline is approximate only. Exact timings of visits relate to the day on enrolment, i.e., each visit must occur at indicated number of days after enrolment ± time window. % Cumulative blood volume for volunteers if blood taken as per schedule, and excluding any repeat safety blood test that may be necessary. [†]Only for the final group which are enrolled

.

Table 3: Schedule of Events for Unscheduled and Early Termination Visits. Applicable for

 both all groups

	Unscheduled Visit Following AE	Early Termination Visit
Medical History	(x)	(x)
Physical Examination	(X) ¹	(x)
ECG	(x)	
Urinalysis	(x)	
Physical Observations	х	х
Concomitant medications	х	х
AEs reviewed	х	х
Diary card review ²	х	(x)
Haematology (mL)	3	3
Biochemistry (mL)	5	5
Coagulation (mL)	(2.7)	(2.7)

(x) = If considered necessary, emphasising any acute complaints.

¹ A full physical examination or symptom directed physical examination can be carried out at the discretion of the investigator.

² Required if the participant is currently within the diary card completion phase of the study only.

The above schedule is not an exhaustive list; procedures carried out will be guided by clinical need and will be at the discretion of the investigator.

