1.4 Pre-clinical studies of pEVAC-PS

1.5. Dose Rationale

The CE-marked PharmaJet Tropis intradermal (ID) delivery of DNA has demonstrated to be highly effective at reducing the dose required for anti-viral responses in several different systems. An adaptive dose escalation regime follows to discover the lowest dose of DNA which will produce an effective immune response when delivered intradermally, with potential doses of 1.2mg, 0.8mg, 0.4mg and 0.2mg.

Objective	Outcome measure			
Primary To assess the safety and reactogenicity of a new pan-Sarbeco Coronavirus DNA candidate vaccine pEVAC-PS in a boosting regime in healthy volunteers.	 a) Occurrence of solicited local reactogenicity signs and symptoms for 7 days following vaccination; b) Occurrence of solicited systemic reactogenicity signs and symptoms for 7 days following vaccination; c) Occurrence of unsolicited adverse events (AEs) for 28 days following vaccination; d) Change from baseline for safety laboratory measures and; e) Occurrence of disease enhancement episodes 			
Secondary To assess the humoral immunogenicity of pEVAC-PS when administered to healthy volunteers as a booster vaccine, through the analysis of SARS-CoV and SARS-CoV-2 RBD antibody titres. To assess the humoral immunogenicity of the candidate vaccine pEVAC-PS at 28 days (4 weeks) after 2 doses of pEVAC-PS have been administered 28 days apart, given by needle-free technology (PharmaJet); both administered in split doses, left and right deltoids (when >0.2mg)	 a) Serology: receptor binding domain (RBD) responses in the majority of vaccinees per group for SARS-CoV and SARS-CoV-2 			
Secondary Assess optimum dosing of candidate vaccine pEVAC-PS	a) Compare dose tolerability and results of immunogenicity of up to four different doses of PharmaJet ID			

2. Objectives and Endpoints

	administration at 28 days (4 weeks)
	after the second dose of vaccine
Secondary	a) Serology: receptor binding domain
To assess long term (up to 12 months)	(RBD) for SARS-CoV and SARS-
humoral immunogenicity of the candidate	CoV-2 RBD pre and post-
vaccine pEVAC-PS administered by the	immunisation.
needle-free technology (PharmaJet)	
administered as 2 doses (split L&R	
when >0.2mg)	

3. Study Design

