3.1.1. Immunogenicity endpoints

The adaptive protocol is based on reviews of immunogenicity data which will be made 4 weeks following the second administration of pEVAC-PS (8 weeks following the first dose). The decision for how to proceed will be made on the basis of the proportion of participants within each group who have seroconverted. Seroconversion will be defined as a positive readout from the SARS-CoV and/or SARS-CoV-2 RBD ELISA. The dose used for each group will be classified as either having met immunogenicity target, failed to meet immunogenicity target, or had very poor / no response. Proportions of participant seroconversion will be classed as the following:

Stage 1 – Meets immunogenicity target if 5 or 6 out of 6 participants have at least a 2-fold increase in Ab titre (at 0.2mg) we proceed to Expanded Group 1.

- Stage 2 (Expanded Group 1) if 12/12 participants have a 2-fold increase in Ab titre (at 0.2mg) consider to re-formulate and reduce the dose for a new study.
- Stage 2 (Expanded Group 1) if 10 or more of the 12 participants have at least a 2-fold increase in Ab titre (at 0.2mg) we select 0.2mg as the optimum dose to move forward into a Phase II study.
- Stage 2 (Expanded Group 1) if <=9 participants have a 2-fold increase in Ab titre (at 0.2mg) then a further 9 participants will be recruited to group 2a (0.4) and 2b (0.8mg) each, to be run in parallel.

 - The study will conclude after running groups 2a and 2b.

Stage 1 – Fails to meet immunogenicity target if only 3 or 4 out of 6 participants have at least a 2-fold increase in Ab titre, then we proceed to Groups 2a (0.4mg) and 2b (0.8mg) in parallel.

- Stage 2 if 7-9 or more participants have a 2-fold increase in Ab titre (at 0.4 or 0.8 mg) we expand whichever group has the higher number of responders. If both groups 2a and 2b have 9 responders, we will expand the lower dose.
- Stage 2 if <7 participants have a 2-fold increase in Ab titre (at 0.4 or 0.8 mg) we move to Stage 3 and increase dose to 1.2mg.

Stage 1 – With a poor response, if 2 or less participants out of 6 have a 2-fold increase in Ab titre, we proceed to Groups 2a (0.8mg) and 2b (1.2mg) in parallel.

- Stage 2 if 7-9 participants have a 2-fold increase in Ab titre (at 0.8 or 1.2mg) we expand whichever group has the higher number of responders.
- Stage 2 if <7 participants have a 2-fold increase in Ab titre at 0.8mg and 1.2mg the trial will conclude.

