5.3.9. Distribution, review and completion of diary cards

Volunteers will be asked to complete a diary card for a period of 2 months following administration of vaccine on Day 0. A separate diary will be issued for each 28 day period post vaccination. An oral thermometer, tape measure and access to a paper diary card for solicited and unsolicited AEs will be given to each volunteer. The diaries will collect information on the timing and severity of the following solicited AEs:

Local solicited AEs	Systemic solicited AEs
Pain	Fever
Redness	Feverishness
Warmth	Joint pains
ltch	Muscle pains
	Fatigue
	Headache
	Nausea
	Malaise

Table 4: Solicited AEs as collected on post vaccination diary cards

Volunteers will be instructed on how to self-assess the severity of these AEs. There will also be space on the diary card to self-document unsolicited AEs, and whether medication was taken to relieve the symptoms.

Volunteers will be asked to bring their diary to the study site at each follow up visit. Diaries will be reviewed by a member of the study team. All diaries will be collected at the Week 8 follow up visit.

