5.7 Duration of Study

Volunteers will be considered to be enrolled in the study on receipt of their first vaccination. Volunteers will remain in the study for a maximum of 18 months (+/- 28 days) after being enrolled (this includes up to 6 months during the recruitment and dosing phase with a follow-up period of up to 12 months).

The study is considered to be complete upon last volunteer/last visit at the site. The end of study is defined as the completion of the testing of samples, to be achieved no later than 12 months after the date of the last visit of the last volunteer.

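### Visits after dose 2 are timed from enrolment although dose 2 may move by 7 days, so the decisive 28-day titre can be drawn 14 to 42 days after dose 2 and the second diary collected after 14 days

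*Protocol*

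**What the plan says.** Table 2 in Section 5.2 calls its timeline approximate, but its footnote then sets a binding rule: "each visit must occur at indicated number of days after enrolment ± time window". Section 5.7 defines the starting point: "Volunteers will be considered to be enrolled in the study on receipt of their first vaccination". For attendances 4 to 9 (Days 3, 7, 14, 28, 42 and 56) the window row reads "Time window (days) ±1 ±2 ±3 ±7 ±3 ±7". Dose 2 is therefore Day 28 ±7, the next visit Day 42 ±3 and the decision visit Day 56 ±7, all counted from dose 1.

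The endpoints are counted from dose 2. The objectives and endpoints table (Section 2) places the humoral assessment "at 28 days (4 weeks) after 2 doses of pEVAC-PS have been administered 28 days apart". Section 3.1.1 bases the adaptive design on "reviews of immunogenicity data which will be made 4 weeks following the second administration of pEVAC-PS", and adds in brackets that this is 8 weeks after the first dose. The primary outcome for unsolicited events is "Occurrence of unsolicited adverse events (AEs) for 28 days following vaccination".

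Section 5.3.9 issues one diary per 28-day period after each dose, yet also states: "All diaries will be collected at the Week 8 follow up visit". No section says that visits after dose 2 move when dose 2 is early, late or deferred.

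**The concern.** The protocol runs two clocks. The endpoints count from dose 2, the visits count from dose 1, and dose 2 itself has a two-week window. A sample can be fully in window and still lie well away from the time point that it is meant to represent.

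This sample decides the course of the trial. Section 3.1.1 routes Stage 1 on whether 5 or 6, 3 or 4, or at most 2 of 6 participants show a 2-fold rise. Later steps turn on 7 of 9 or 10 of 12. One participant separates 4/6 from 5/6, or 2/6 from 3/6, and so determines which doses are tested next. Section 3.1.1 also expands whichever of groups 2a and 2b has more responders, and those groups could differ in when they were sampled. If titres move between the earliest and latest permitted day, part of a responder count would reflect scheduling rather than dose.

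Two safety inputs are exposed in the same way: the timing of the laboratory tests after dose 2, and how much of the 28 days after dose 2 the diary covers.

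**Working it through.** **Inputs (Table 2; Section 5.7 for Day 0)**
- Day 0 = enrolment = first vaccination.
- Dose 2 (attendance 7): Day 28 ±7, so Days 21 to 35.
- Attendance 8: Day 42 ±3, so Days 39 to 45.
- Attendance 9 (Week 8, decision sample): Day 56 ±7, so Days 49 to 63.
- Attendance 10: Day 84 ±3, so Days 81 to 87.

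**The plan's own figure.** 56 − 28 = 28 days. The stated 4 weeks after dose 2, equal to 8 weeks after dose 1, is reproduced at the nominal dates.

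**Range allowed by the windows.** Shortest interval = earliest visit day − latest dose 2 day. Longest interval = latest visit day − earliest dose 2 day.

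| Visit | Shortest after dose 2 | Nominal | Longest after dose 2 |
|---|---|---|---|
| Day 42 ±3 | 39 − 35 = 4 | 14 | 45 − 21 = 24 |
| Day 56 ±7 | 49 − 35 = 14 | 28 | 63 − 21 = 42 |
| Day 84 ±3 | 81 − 35 = 46 | 56 | 87 − 21 = 66 |

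The biochemistry and haematology row marks one attendance after the dose 2 visit, Day 42. (The Day 84 total of 55 mL is 5 mL above the one blood row marked there, so this reading rests on the row itself.) At the 4-day extreme, that visit comes before the 7-day solicited period has ended.

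**How common, as an illustration only.** Dose 2 and the Day 56 visit each have 15 permitted days, giving 15 × 15 = 225 pairs. Suppose all pairs were equally likely:
- More than 7 days away from 28: 2 × (7+6+5+4+3+2+1) = 56 pairs, and 56/225 = 24.9%.
- Before day 28 after dose 2: (225 − 15)/2 = 105 pairs, and 105/225 = 46.7%.

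**Can a site satisfy both clocks?**
- Day 56 visit: 21 + 28 = 49 and 35 + 28 = 63, exactly the limits of Day 56 ±7. A sample at dose 2 + 28 is always permitted, but it is not required.
- Day 42 visit: dose 2 + 14 lies inside Days 39 to 45 only if dose 2 falls on Days 25 to 31 (39 − 14 = 25; 45 − 14 = 31). Outside those days the visit cannot track dose 2 and stay in window.

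**Diary.** With dose 2 on Day 35 and the Week 8 visit on Day 49, the diary is handed in 14 days after dose 2, and 28 − 14 = 14 days are not covered. The next scheduled enquiry about adverse events is the Day 84 visit, 46 to 66 days after dose 2.

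**With the visit anchored to dose 2 and the same ±7.** 28 − 7 = 21 and 28 + 7 = 35. The spread falls from 42 − 14 = 28 days to 35 − 21 = 14 days. A diary handed in at day 21 would still be 28 − 21 = 7 days short, so re-anchoring alone does not settle the diary.

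**The case against.** The best defence is that schedule and endpoint are compatible for the decision visit. Whatever day in the window dose 2 is given, dose 2 + 28 lies within Day 56 ±7, and a site that reads Sections 2 and 3.1.1 would aim for it. The 14- and 42-day extremes need two maximal shifts in opposite directions. Even under equal weighting, about 75% of samples fall within 21 to 35 days. The analysis is descriptive, Section 8.1 lets the investigators use all available tolerability and immunogenicity information, and immunology blood is also drawn at Day 42.

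Much of this stands. A reader might infer that the schedule contradicts the endpoint outright; for the Day 56 visit it does not. What remains is that the one binding scheduling rule points to the wrong date and leaves dose 2 + 28 optional, and that the Day 42 visit cannot always follow dose 2. The SAP can define analysis windows, but it cannot retime a sample already drawn.

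A reader might also infer that the 28-day adverse event window is halved. The protocol does not support that. Section 7.6.1 requires recording of all adverse events in the 28 days after each vaccination, and Table 2 asks about them again at Day 84 and later. Solicited events run for 7 days, so even a 14-day diary covers them. Only prospective diary capture of days 15 to 28 can be lost, leaving those days to recall.

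**Conclusion.** The concern holds as a fault in how visits are anchored. Without any deviation, the decision sample can be taken 14 to 42 days after dose 2 (nominal 28), the marked post-dose-2 safety bloods 4 to 24 days after it, and the second diary can hold as few as 14 of its 28 days. These are limits that the windows allow, not expected values. The 24.9% and 46.7% shares rest on an assumption of equal likelihood made only for illustration. If a dose deferred under Section 5.6 were given after Day 35 and later visits stayed on the enrolment clock, the interval would be shorter still.

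It would be going too far to say that dose decisions will be wrong or that any 2-fold call would flip. The protocol gives no titre kinetics for this vaccine between days 14 and 42, so neither the direction nor the size of an effect can be stated. The case for acting is that the responder cut-offs can turn on one participant and the remedy is cheap.

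**What to change.** Change the Table 2 footnote so that attendances 8 and 9, and preferably all later ones, are timed from the actual date of dose 2: attendance 8 at dose 2 + 14 ±3 days and attendance 9 at dose 2 + 28 ±7 days. Align the bracketed 8-week equivalence in Section 3.1.1 by marking it as nominal.

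Reword Section 5.3.9 so that the second diary is completed through day 28 after dose 2. If the Week 8 visit comes earlier, the diary is returned afterwards, by post or at the next attendance. This is needed because the retained ±7 window still allows a visit on day 21.

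The cost is one footnote, one or two sentences and the scheduling tool. Some visits move by up to 7 calendar days and some diaries come back later. No visits or samples are added. The decision sample would still vary over 14 days, half the present spread.

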5.3 Study Procedures

5.3.1. Medical History

A detailed medical history will be taken at set study visits as outlined in the schedule of events, including recent acute illness or events which could constitute AEs.

5.3.2. Physical examination

A detailed physical examination including review of vital systems will be performed at set study visits as outlined in the schedule of attendances. On occasions where a physical exam is carried out as determined by clinical need, these will be either a full physical examination or symptom directed physical examination at the discretion of the investigator.

5.3.3. Physical Observations

Pulse, blood pressure and body temperature will be measured at the time points indicated in the schedule of attendances. Height and weight will be measured at screening only.

5.3.4 Concomitant Medications

Concomitant medications administered up to 30 days before screening must be recorded in the eCRF at the screening visit. Concomitant medications will be recorded prior to vaccine administration at vaccination visits and at each follow up visit. Volunteers will be asked to record any medication that they have taken in their diary card for 28 days post each vaccine administration.

Receipt of any IMP (including experimental vaccines other than the study vaccine) during the study is not allowed.

5.3.5. Blood Tests

Blood will be drawn for the following laboratory tests and processed:

1. At University Hospital Southampton NHS Foundation Trust Laboratories, using NHS standard procedures:

- Haematology; Full Blood Count.
- **Biochemistry;** Sodium, Potassium, Urea, Creatinine, Albumin, Liver Function, Magnesium and Cholesterol.
- **Diagnostic serology;** HBsAg, HCV antibodies, HIV antibodies (specific consent will be gained prior to testing blood for these blood-borne viruses).
- β-HCG serum (female volunteers only)

2. At LVZ laboratories:

Immunology: Serological analysis of antibody responses (such as ELISA); B cell assays. Other immunological assays including flow cytometry, pseudotype neutralisation for Sarbeco viruses, amongst others, and T-cell assays may be performed at the discretion of the Investigators.

5.3.6. Urinalysis

Urine will be tested for blood, protein and glucose at screening. For female volunteers only, urine will be tested for beta-human chorionic gonadotrophin (HCG) at screening and immediately prior to each vaccination.

5.3.7. Pregnancy testing

For female volunteers only, a serum beta-human chorionic gonadotrophin (β HCG) test will be carried out at screening and urine will be tested for β HCG prior to each vaccination.

5.3.8. Administration of vaccines

Before each vaccination, the on-going eligibility of the volunteer and contraindications will be reviewed. The vaccine will be administered as described in **Section 6.3** *'Dosage and administration of study vaccine'*. The injection site will be covered with a sterile dressing and the volunteer will stay in the clinical area for 60 minutes (+15/-5 minutes) post vaccination. The sterile dressing will be removed and injection site inspected at 30 minutes (+15/-5 minutes)

post vaccination. Observations will be taken at 30 minutes (+/- 5 minutes) post vaccination and at 60 minutes (+15/-5 minutes) post vaccination.

5.3.9. Distribution, review and completion of diary cards

Volunteers will be asked to complete a diary card for a period of 2 months following administration of vaccine on Day 0. A separate diary will be issued for each 28 day period post vaccination. An oral thermometer, tape measure and access to a paper diary card for solicited and unsolicited AEs will be given to each volunteer. The diaries will collect information on the timing and severity of the following solicited AEs:

Local solicited AEs	Systemic solicited AEs
Pain	Fever
Redness	Feverishness
Warmth	Joint pains
ltch	Muscle pains
	Fatigue
	Headache
	Nausea
	Malaise

Table 4: Solicited AEs as collected on post vaccination diary cards

Volunteers will be instructed on how to self-assess the severity of these AEs. There will also be space on the diary card to self-document unsolicited AEs, and whether medication was taken to relieve the symptoms.

Volunteers will be asked to bring their diary to the study site at each follow up visit. Diaries will be reviewed by a member of the study team. All diaries will be collected at the Week 8 follow up visit.

